72 DIURETICS CONGESTIVE HEART FAILURE BUMETANIDE				
	73	DIURETICS		FUROSEMIDE

	Medication Class (WHOATC2)	Indication (CMINDC)	WHOGEN
74	DIURETICS	CONGESTIVE HEART FAILURE	HYDROCHLOROTHIAZIDE
75	DIURETICS	CONGESTIVE HEART FAILURE	METOLAZONE
76	DIURETICS	CONGESTIVE HEART FAILURE	SPIRONOLACTONE
77	DIURETICS	CORONARY ARTERY DISEASE	HYDROCHLOROTHIAZIDE
78	DIURETICS	CORONARY ARTERY DISEASE.	FUROSEMIDE
79	DIURETICS	ELEVATION OF BLOOD PRESSURE	FUROSEMIDE
80	DIURETICS	MITRAL INSUFFICIENCY	TORASEMIDE
81	DIURETICS	TRANSGENGER	SPIRONOLACTONE
82	LIPID MODIFYING AGENTS	ACUTE MYOCARDIAL INFARCTION	ATORVASTATIN CALCIUM
83	LIPID MODIFYING AGENTS	ACUTE MYOCARDIAL INFARCTION	OMEGA 3 TRIGLYCERIDES
84	LIPID MODIFYING AGENTS	ATHEROSCLEROTIC HEART DISEASE OF NATIVE CORONARY ARTERY WITHOUT ANGINA PECTORIS	SIMVASTATIN
85	LIPID MODIFYING AGENTS	BASILAR ARTERY THROMBUS	ATORVASTATIN CALCIUM
86	LIPID MODIFYING AGENTS	CAD	PRAVASTATIN SODIUM
87	LIPID MODIFYING AGENTS	CAD	ROSUVASTATIN CALCIUM
88	LIPID MODIFYING AGENTS	CARDIAC PROPHYLAXIS	ATORVASTATIN
89	LIPID MODIFYING AGENTS	CARDIAC PROPHYLAXIS	FISH OIL
90	LIPID MODIFYING AGENTS	CARDIOVASCULAR PROPHYLAXIS	ATORVASTATIN CALCIUM
91	LIPID MODIFYING AGENTS	CHEST TIGHTNESS	ATORVASTATIN

	Medication Class (WHOATC2)	Indication (CMINDC)	WHOGEN
Hypei	rlipidemia (HLIPDEM)		
1	AGENTS ACTING ON THE RENIN ANGIOTENSIN SYSTEM	HYPERTRIGLYCERIDEMIA	LISINOPRIL
2	ANTIHYPERTENSIVES	HYPERCHOLESTEROLEMIA	DOXAZOSIN MESILATE
3	CARDIAC THERAPY	HYPERCHOLESTEROLEMIA	UBIDECARENONE
4	LIPID MODIFYING AGENTS	ABNORMAL LIPIDS	ATORVASTATIN
5	LIPID MODIFYING AGENTS	CARDIAC PROPHYLAXIS	ROSUVASTATIN
6	LIPID MODIFYING AGENTS	CHOLESTEROL	ROSUVASTATIN
7	LIPID MODIFYING AGENTS	CHOLESTEROL	ROSUVASTATIN CALCIUM
8	LIPID MODIFYING AGENTS	CHOLESTEROLEAMIA	ATORVASTATIN
9	LIPID MODIFYING AGENTS	CHOLESTERORL	ROSUVASTATIN CALCIUM
10	LIPID MODIFYING AGENTS	CORONARY ARTERY DISEASE	ATORVASTATIN
11	LIPID MODIFYING AGENTS	CORONARY ARTERY DISEASE	EZETIMIBE
12	LIPID MODIFYING AGENTS	CORONARY ARTERY DISEASE	FENOFIBRATE
13	LIPID MODIFYING AGENTS	CORONARY ARTERY DISEASE	ROSUVASTATIN CALCIUM
14	LIPID MODIFYING AGENTS	CORONARY ARTERY DISEASE PROPHYLAXIS	ATORVASTATIN
15	LIPID MODIFYING AGENTS	DIET SUPPLEMENT	FISH OIL
16	LIPID MODIFYING AGENTS	DIETARY SUPPLEMENT	FISH OIL
17	LIPID MODIFYING AGENTS	DIETARY SUPPLEMENTS	FISH OIL
18	LIPID MODIFYING AGENTS	DYSLIPEDEMIA	ROSUVASTATIN CALCIUM
19	LIPID MODIFYING AGENTS	DYSLIPIDAEMIA	ATORVASTATIN
20	LIPID MODIFYING AGENTS	DYSLIPIDEMIA	ATORVASTATIN
21	LIPID MODIFYING AGENTS	DYSLIPIDEMIA	FENOFIBRATE
22	LIPID MODIFYING AGENTS	DYSLIPIDEMIA	FISH OIL
23	LIPID MODIFYING AGENTS	DYSLIPIDEMIA	GEMFIBROZIL
24	LIPID MODIFYING AGENTS	DYSLIPIDEMIA	PRAVASTATIN
25	LIPID MODIFYING AGENTS	DYSLIPIDEMIA	ROSUVASTATIN
26	LIPID MODIFYING AGENTS	DYSLIPIDEMIA, WORSENING	ROSUVASTATIN
27	LIPID MODIFYING AGENTS	DYSLIPIDERMIA	PRAVASTATIN
28	LIPID MODIFYING AGENTS	ELEVATED CHOLESTEROL	SIMVASTATIN
29	LIPID MODIFYING AGENTS	ELEVATED LIPIDS	ATORVASTATIN
30	LIPID MODIFYING AGENTS	ELEVATED LIPIDS	ATORVASTATIN CALCIUM
31	LIPID MODIFYING AGENTS	ELEVATED TRIGLYCERIDES	FISH OIL
32	LIPID MODIFYING AGENTS	HIGH CHOLESTEROL	ATORVASTATIN
33	LIPID MODIFYING AGENTS	HIGH CHOLESTEROL	ATORVASTATIN CALCIUM
34	LIPID MODIFYING AGENTS	HIGH CHOLESTEROL	GEMFIBROZIL
35	LIPID MODIFYING AGENTS	HIGH CHOLESTEROL	LOVASTATIN
36	LIPID MODIFYING AGENTS	HIGH CHOLESTEROL	PRAVASTATIN
37	LIPID MODIFYING AGENTS	HIGH CHOLESTEROL	ROSUVASTATIN CALCIUM
38	LIPID MODIFYING AGENTS	HIGH CHOLESTEROL	SIMVASTATIN
39	LIPID MODIFYING AGENTS	HIGH CHOLESTROL	ATORVASTATIN
40	LIPID MODIFYING AGENTS	HIGH PLASMA LIPIDS	ATORVASTATIN
41	LIPID MODIFYING AGENTS	HIGH TRIGLYCERIDES	FENOFIBRATE
42	LIPID MODIFYING AGENTS	HIGH TRIGLYCERIDES AND HYPERCHOLESTEROLEMIA	ATORVASTATIN
43	LIPID MODIFYING AGENTS	HIPERCOLESTEROLEMIA	ATORVASTATIN

	Medication Class (WHOATC2)	Indication (CMINDC)	WHOGEN
44	LIPID MODIFYING AGENTS	HIPERCOLESTEROLEMIA	ATORVASTATIN CALCIUM
45	LIPID MODIFYING AGENTS	HIPERCOLESTEROLEMIA	SIMVASTATIN
46	LIPID MODIFYING AGENTS	HYERLIPIDEMIA	OMEGA 3 ACID ETHYL ESTER
47	LIPID MODIFYING AGENTS	HYPERCHOLESTERIMIA	FENOFIBRATE
48	LIPID MODIFYING AGENTS	HYPERCHOLESTERINAEMIA	ATORVASTATIN
49	LIPID MODIFYING AGENTS	HYPERCHOLESTERINAEMIA	PRAVASTATIN
50	LIPID MODIFYING AGENTS	HYPERCHOLESTERINEMIA	PRAVASTATIN
51	LIPID MODIFYING AGENTS	HYPERCHOLESTERINEMIA	SIMVASTATIN
52	LIPID MODIFYING AGENTS	HYPERCHOLESTEROL	PRAVASTATIN
53	LIPID MODIFYING AGENTS	HYPERCHOLESTEROLAEMIA	ATORVASTATIN
54	LIPID MODIFYING AGENTS	HYPERCHOLESTEROLAEMIA	PRAVASTATIN
55	LIPID MODIFYING AGENTS	HYPERCHOLESTEROLAEMIA	ROSUVASTATIN
56	LIPID MODIFYING AGENTS	HYPERCHOLESTEROLAEMIA	SIMVASTATIN
57	LIPID MODIFYING AGENTS	HYPERCHOLESTEROLEMIA	ATORVASTATIN
58	LIPID MODIFYING AGENTS	HYPERCHOLESTEROLEMIA	ATORVASTATIN CALCIUM
59	LIPID MODIFYING AGENTS	HYPERCHOLESTEROLEMIA	EZETIMIBE
60	LIPID MODIFYING AGENTS	HYPERCHOLESTEROLEMIA	FENOFIBRATE
61	LIPID MODIFYING AGENTS	HYPERCHOLESTEROLEMIA	FISH OIL
62	LIPID MODIFYING AGENTS	HYPERCHOLESTEROLEMIA	LOVASTATIN
63	LIPID MODIFYING AGENTS	HYPERCHOLESTEROLEMIA	PITAVASTATIN CALCIUM
64	LIPID MODIFYING AGENTS	HYPERCHOLESTEROLEMIA	PRAVASTATIN
65	LIPID MODIFYING AGENTS	HYPERCHOLESTEROLEMIA	PRAVASTATIN SODIUM
66	LIPID MODIFYING AGENTS	HYPERCHOLESTEROLEMIA	ROSUVASTATIN
67	LIPID MODIFYING AGENTS	HYPERCHOLESTEROLEMIA	ROSUVASTATIN CALCIUM
68	LIPID MODIFYING AGENTS	HYPERCHOLESTEROLEMIA	SIMVASTATIN
69	LIPID MODIFYING AGENTS	HYPERCHOLESTEROLEMIA (PURE) AND MIXED HYPERLIPIDEMIA	ROSUVASTATIN CALCIUM
70	LIPID MODIFYING AGENTS	HYPERCHOLESTEROLMIA	PRAVASTATIN SODIUM
71	LIPID MODIFYING AGENTS	HYPERCHOLESTROLEMIA	ATORVASTATIN
72	LIPID MODIFYING AGENTS	HYPERCHOLESTROLEMIA	ATORVASTATIN CALCIUM
73	LIPID MODIFYING AGENTS	HYPERCHOLESTROLEMIA	FENOFIBRATE
74	LIPID MODIFYING AGENTS	HYPERCHOLSTEROAEMIA	ATORVASTATIN CALCIUM
75	LIPID MODIFYING AGENTS	HYPERCOLESTEROLEMIA	SIMVASTATIN
76	LIPID MODIFYING AGENTS	HYPERLIDEMIA	ROSUVASTATIN CALCIUM
77	LIPID MODIFYING AGENTS	HYPERLIDIPEMIA	ATORVASTATIN
78	LIPID MODIFYING AGENTS	HYPERLIPDEMIA	ROSUVASTATIN CALCIUM
79	LIPID MODIFYING AGENTS	HYPERLIPEDMIA MIXED	ATORVASTATIN
80	LIPID MODIFYING AGENTS	HYPERLIPIDAEMIA	ATORVASTATIN
81	LIPID MODIFYING AGENTS	HYPERLIPIDAEMIA	FENOFIBRATE
82	LIPID MODIFYING AGENTS	HYPERLIPIDAEMIA	PRAVASTATIN
83	LIPID MODIFYING AGENTS	HYPERLIPIDAEMIA	PRAVASTATIN SODIUM
84	LIPID MODIFYING AGENTS	HYPERLIPIDAEMIA	ROSUVASTATIN
85	LIPID MODIFYING AGENTS	HYPERLIPIDAEMIA	ROSUVASTATIN CALCIUM
86	LIPID MODIFYING AGENTS	HYPERLIPIDEMA	ATORVASTATIN
87	LIPID MODIFYING AGENTS	HYPERLIPIDEMIA	ATORVASTATIN
88	LIPID MODIFYING AGENTS	HYPERLIPIDEMIA	ATORVASTATIN CALCIUM

# Statistical Analysis Plan – End of Blinded Treatment Phase Analysis

	Medication Class (WHOATC2)	Indication (CMINDC)	WHOGEN
89	LIPID MODIFYING AGENTS	HYPERLIPIDEMIA	COLESEVELAM HYDROCHLORIDE
90	LIPID MODIFYING AGENTS	HYPERLIPIDEMIA	EICOSAPENTAENOIC ACID ETHYL ESTER
91	LIPID MODIFYING AGENTS	HYPERLIPIDEMIA	EZETIMIBE
92	LIPID MODIFYING AGENTS	HYPERLIPIDEMIA	FENOFIBRATE
93	LIPID MODIFYING AGENTS	HYPERLIPIDEMIA	FENOFIBRIC ACID
94	LIPID MODIFYING AGENTS	HYPERLIPIDEMIA	FISH OIL
95	LIPID MODIFYING AGENTS	HYPERLIPIDEMIA	GEMFIBROZIL
96	LIPID MODIFYING AGENTS	HYPERLIPIDEMIA	LOVASTATIN
97	LIPID MODIFYING AGENTS	HYPERLIPIDEMIA	OMEGA 3 ACID ETHYL ESTER
98	LIPID MODIFYING AGENTS	HYPERLIPIDEMIA	PELAGO
99	LIPID MODIFYING AGENTS	HYPERLIPIDEMIA	PRAVASTATIN
100	LIPID MODIFYING AGENTS	HYPERLIPIDEMIA	PRAVASTATIN SODIUM
101	LIPID MODIFYING AGENTS	HYPERLIPIDEMIA	ROSUVASTATIN
102	LIPID MODIFYING AGENTS	HYPERLIPIDEMIA	ROSUVASTATIN CALCIUM
103	LIPID MODIFYING AGENTS	HYPERLIPIDEMIA	SIMVASTATIN
104	LIPID MODIFYING AGENTS	HYPERLIPIDEMIA PREVENTION	ROSUVASTATIN CALCIUM
105	LIPID MODIFYING AGENTS	HYPERLIPIDEMIA,	PRAVASTATIN
106	LIPID MODIFYING AGENTS	HYPERLIPIDEMIA, MIXED	ATORVASTATIN CALCIUM
107	LIPID MODIFYING AGENTS	HYPERLIPIDEMIA, MIXED	FENOFIBRATE
108	LIPID MODIFYING AGENTS	HYPERTENSION	ATORVASTATIN
109	LIPID MODIFYING AGENTS	HYPERTENSION	PRAVASTATIN
110	LIPID MODIFYING AGENTS	HYPERTRIGLYCERDEMIA	ATORVASTATIN
111	LIPID MODIFYING AGENTS	HYPERTRIGLYCERIDEMIA	ATORVASTATIN CALCIUM
112	LIPID MODIFYING AGENTS	HYPERTRIGLYCERIDEMIA	FENOFIBRATE
113	LIPID MODIFYING AGENTS	HYPERTRIGLYCERIDEMIA	FENOFIBRIC ACID
114	LIPID MODIFYING AGENTS	HYPERTRIGLYCERIDEMIA	FIBRATES
115	LIPID MODIFYING AGENTS	HYPERTRIGLYCERIDEMIA	FISH OIL
116	LIPID MODIFYING AGENTS	HYPERTRIGLYCERIDEMIA	OMEGA 3 TRIGLYCERIDES
117	LIPID MODIFYING AGENTS	HYPERTRIGLYCERIDEMIA	PRAVASTATIN
118	LIPID MODIFYING AGENTS	HYPERTRIGLYCERIDEMIA,HYPE RCHOLESTEROLEMIA	ATORVASTATIN
119	LIPID MODIFYING AGENTS	HYPERTRIGLYERIDEMIA	GEMFIBROZIL
120	LIPID MODIFYING AGENTS	HYPERTRYGLYCERIDEMIA	PRAVASTATIN
121	LIPID MODIFYING AGENTS	INDICATION HYPERLIPIDEMIA	FENOFIBRATE
122	LIPID MODIFYING AGENTS	IRRITABLE BOWEL SYNDROME	FISH OIL
123	LIPID MODIFYING AGENTS	ISCHEMIC HEART DISEASE	ROSUVASTATIN CALCIUM
124	LIPID MODIFYING AGENTS	LDL CHOLESTEROL GRADE 3 ELEVATION	ROSUVASTATIN
125	LIPID MODIFYING AGENTS	MIXED DYSLIPIDEMIA	FENOFIBRATE
126	LIPID MODIFYING AGENTS	MIXED DYSLIPIDEMIA	ROSUVASTATIN CALCIUM
127	LIPID MODIFYING AGENTS	MIXED HYPERLIPDEMIA	ATORVASTATIN
128	LIPID MODIFYING AGENTS	MIXED HYPERLIPIDEMIA	ATORVASTATIN
129	LIPID MODIFYING AGENTS	MIXED HYPERLIPIDEMIA	FENOFIBRATE
130	LIPID MODIFYING AGENTS	MIXED HYPERLIPIDEMIA	GEMFIBROZIL
131	LIPID MODIFYING AGENTS	NUTRITION SUPPLEMENT	FISH OIL

	Medication Class (WHOATC2)	Indication (CMINDC)	WHOGEN
132	LIPID MODIFYING AGENTS	NUTRITIONAL SUPPLEMENT	FISH OIL
133	LIPID MODIFYING AGENTS	NUTRITIONAL SUPPLEMENT	OMEGA 3 FATTY ACIDS
134	LIPID MODIFYING AGENTS	PREVENTATIVE FOLLOWING ACUTE MYCARDIAL INFARCTION	ATORVASTATIN
135	LIPID MODIFYING AGENTS	PREVENTION FOR HYPERCHOLESTEROLEMIA	OMEGA 3 FATTY ACIDS
136	LIPID MODIFYING AGENTS	PREVENTIVE	FISH OIL W/LINUM USITATISSIMUM SEED OIL
137	LIPID MODIFYING AGENTS	PROPHYLAXIS	FISH OIL
138	LIPID MODIFYING AGENTS	PURE HYPERCHOLESTEROLEMIA	ATORVASTATIN
139	LIPID MODIFYING AGENTS	SECONDARY STROKE PREVENTION	ATORVASTATIN
140	LIPID MODIFYING AGENTS	STROKE PROPHYLAXIS	ATORVASTATIN
141	LIPID MODIFYING AGENTS	SUPPLEMENT	FISH OIL
142	LIPID MODIFYING AGENTS	SUPPLEMENT	OMEGA 3 6 9
143	LIPID MODIFYING AGENTS	SUPPLEMENT	OMEGA 3 FATTY ACIDS
144	LIPID MODIFYING AGENTS	SUPPLEMENT	OMEGA 3 FATTY ACIDS W/OMEGA 6 FATTY ACIDS
145	LIPID MODIFYING AGENTS	SUPPLEMENT	OMEGA 3 ACID ETHYL ESTER
146	LIPID MODIFYING AGENTS	SUPPLEMENT/HYPERLIPIDEMIA	FISH OIL
147	LIPID MODIFYING AGENTS	SUPPLEMENTAL USE	FISH OIL
148	LIPID MODIFYING AGENTS	SUPPLEMETN	FISH OIL
149	LIPID MODIFYING AGENTS	UNCONTROLLED DIABETES MELLITUS 2	ATORVASTATIN
150	LIPID MODIFYING AGENTS	WORSENING HYPERLIPIDEMIA	ATORVASTATIN
151	LIPID MODIFYING AGENTS	WORSENING OF HYPERLIPIDEMIA	FISH OIL
152	LIPID MODIFYING AGENTS	HIGH CHOLESTEROL	NICOTINIC ACID
153	LIPID MODIFYING AGENTS	HYPERCHOLESTEROLEMIA	NICOTINIC ACID
154	LIPID MODIFYING AGENTS	HYPERLIPIDEMIA	NICOTINIC ACID
155	LIPID MODIFYING AGENTS	MIXED HYPERLIPIDEMIA	NICOTINIC ACID

## **Appendix 12. Programming Specification**

- 1) AGE calculated as follows:
  - a) AGE (years) is calculated from the number of days between the date of birth (DOB) and Day 1 (first dose date),
  - b) Use the SAS INTCK function to determine the number of "1st-of-month days" (ie, January 1st, February 1st, March 1st) between DOB and Day 1 (inclusive),
  - c) Divide the result in (b) by 12,
  - d) AGE the integer of the result in (c),
  - e) If the DOB and Day 1 have the month in common and the birthday is later in the month than the date of Study Day 1, then subtract one from the AGE result above.
- 2) For subjects randomized and never dosed with study drug, age will be calculated from the date of randomization.
- 3) All screened subjects refer to all subjects who are screened (ie, with nonmissing screening date) and have a screening number. For summaries, the same subject is counted only once. DOB and other demographic information such as sex, race, ethnicity, country, and initials will be used to identify unique screened subjects.
- 4) Screen failure subjects are the subjects who are screened and answered "No" for any inclusion criteria or "Yes" for any exclusion criteria regardless of which version of protocol the subject was consent to.
- 5) Subjects in the randomized analysis set are defined as subjects randomized into the study. IXRSRAND is the source to determine whether the subject is randomized (ie, subject with nonmissing RGMNDTN in the IXRSRAND dataset) and confirmed by the eCRF ENROLL dataset (ie, ENROLLYN "Yes" in ENROLL dataset).
- 6) Randomized treatment (ie, TRT01P in ADSL) is derived from IXRSRAND, while actual treatment received (ie, TRT01A in ADSL) is assigned as the randomized treatment if subject took at least 1 dose of study drug and assigned as blank if subject never dosed.
- 7) In disposition table, the reasons for premature discontinuation are displayed in the order as they appear on the eCRF.

- 8) Only 1 study completion form is collected for the entire study. Therefore, study disposition in the DB phase of the study is defined as follows for dosed subjects:
  - f) Subjects who completed study in the DB phase are defined as follows:
    - i) Open-label entry eCRF marked as "Yes", OR
    - ii) Open-label phase first dose date is present, OR
    - iii) Study completion form is marked as "Yes".
  - g) Subjects who are ongoing in the DB phase of the study is defined as subjects who have not entered the OLE phase of the study, DB phase study drug completion form is marked as "N" or missing, and study completion form is also missing.
  - h) Subjects not meeting (a) and (b) above will be the subjects who discontinued study in the DB phase of the study.
- 9) Body mass index (BMI) will be calculated only at baseline as follows:
- BMI (weight [kg]) / (height [meters])

Baseline height and weight will be used for this calculation.

- 10) For summaries using the PK Case-Control Analysis Set by HIV infection cases versus uninfected matched controls, if one subject serves as both as case and control, this subject will be summarized under both the HIV infection case and uninfected matched control columns.
- 11) SAS codes for the treatment comparison for demographics and baseline characteristics tables.
  - i) CMH test for nominal variable (Y), the p-value from general association test should be used for nominal variable (including race, ethnicity, education, employment, sexuality, number of subjects with a syphilis diagnosis, circumcision, geography, and dichotomous variables):

```
proc freq data=adsl;
   tables trtgrp * Y /cmh /*general association test*/
run;
```

j) CMH test for ordinal variable (Y), the p-value from row mean score test should be used for ordinal variable (including the number of subjects with each STI lab test result type, ongoing relationship, AUDIT questions or total score, proteinuria toxicity grade by urinalysis and categorical summaries of any continuous variables like age, adherence rate or number of partners):

```
proc freq data=adsl;
   tables trtgrp * Y / cmh2 score=modridit; /*row mean score test*/
run:
```

k) Wilcoxon rank sum test for continuous variable (Y), the p-value from the normal approximation 2-sided test should be used for continuous variable:

```
proc npar1way wilcoxon data=adsl;
  class trtgrp;
  var Y;
run;
```

1) Van Elteren test stratified by baseline F/TDF for PrEP:

```
proc freq data=test;
table bftdf*trt*outcome/cmh2 scores=modridit;
run;
```

Where bftdf is baseline F/TDF for PrEP (yes or no), trt is treatment, and outcome is the % change or change from baseline depending on endpoint of interest. Please report p-value from row mean scores differ.

- 12) Please note, "Not Permitted", "Unknown", "Not Applicable", "Not Done" or missing categories will be excluded for percentage calculation and also excluded for p-value generation for categorical data analysis (ie, CMH test or Fisher exact test). For the number of subjects with each syphilis stage and syphilis status summarized among subjects with a syphilis diagnosis, no p-values will be generated.
- 13) SAS code for the treatment comparison for duration of exposure. The p-value from log rank test should be used.

```
proc lifetest data=ADSL method=km;
   time TRTDURD*ESDD(0); /*Derive ESDD from COMT01FL, where ESDD = 0
   indicates censored observation (ie, subject is still on study drug)*/
   Strata TRT01AN;
   label TRTDURD = "Duration of Exposure (Days)";
run;
```

- 14) Last Dose Date and Last Study Date
  - a) Last Dose Date (ie, TRTEDTC, TRTEDT, TR01EDT or TR01EDTC) in ADSL was defined in Section 3.8.1 for subjects who prematurely discontinued or completed study drug in the 'blinded treatment' study phase.

If study drug start date or end date are partially missing (ie, only year and month are known), the day will be imputed as 15 for the purpose of this analysis.

For subjects with a partial last dosing date (ie, month and year of last dose are known), use the max (the dispensing dates of study drug bottles, study drug start dates and end dates, imputed end date of last dose [day imputed as 15]) as the final imputed last dose date. (However, if dispensing date's month is after last dose date's month, data query is needed.)

For subjects where only the year of the last dosing date is known), then impute the last dose date based on the below:

Condition	Last dose date (year only) is imputed as
The year of the last dose is equal to the year of the last visit*	Maximum of study drug start dates and end dates, clinic visit dates and laboratory visit dates excluding the 30-day follow-up visit
The year of the last dose is before the year of the last visit*	December 31st of the last dose year
The year of the last dose is after the year of the last visit*	Data query is needed. If this remains unchanged after query, impute as:  January 1 st of the last dose year

\*Last visit is defined as the maximum of clinic visit dates and laboratory visit dates excluding the 30 day follow up visit.

If the date of last dose is completely missing, use the maximum of study drug start dates and end dates, clinic visit dates, and laboratory visit dates excluding the 30-day follow-up visit to impute the last dose date.

If subject died and the death date is complete (ie, not partial date) and before the imputed last dose date, the complete death date should be used as the imputed last dose date.

If subject has been diagnosed with HIV infection and before the imputed last dose date (year only or month/year only known), the date of HIV diagnosis should be used as the imputed last dose date. Per study design, subjects that have been diagnosed with HIV infection must immediately discontinue study drug.

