## 3.1.3. Per Protocol Analysis Set

The **Per Protocol (PP) Analysis Set** will consist of all subjects in the FAS excluding those with any of the major protocol violations listed below. Subjects will be grouped according to the treatment they actually received. The PP analysis set will be used for an on study drug PrEP treatment (on-treatment) HIV infection sensitivity analyses of the primary endpoint.

PP analysis set will exclude (from FAS) subjects meeting any of the following criteria:

- Subjects where evidence suggests that they have pre-existing HIV that was contracted prior
  to first dose date of study drug (defined as subjects for whom HIV infection prior to first
  dose date of study drug cannot be excluded as the subjects did not have a Covance HIV
  antibody or HIV-1 RNA test analyzed between first dose date (inclusive) and prior to the
  date of diagnosis of HIV infection) based on Gilead's evaluation
- Subjects vaccinated for HIV (identified from the Medical History eCRF or Non-Study ARV Medication eCRF)
- Subjects who meet the exclusion criterion for receiving ongoing therapy with any of the medications listed in the table in protocol Section 5.4 including drugs not to be used with FTC and TAF

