# 3.1.4. Safety Analysis Set

The **Safety Analysis Set** will include all subjects who (1) are randomized into the study and (2) have received at least 1 dose of study drug.

Subjects will be grouped according to the treatment they actually received. This is the primary analysis set for safety analyses.

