## 3.2. Subject Grouping

For analyses based on the All Randomized Analysis Set or the FAS, subjects will be grouped according to the treatment to which they were randomized. For other analyses, subjects will be grouped by actual treatment received. The actual treatment received will differ from the randomized treatment only when the actual treatment received differs from randomized treatment for the entire treatment duration.

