# 4.3. Protocol Deviations

A summary will present the number and percentage of subjects who did not meet at least 1 eligibility criterion and the number of subjects who did not meet specific criteria by treatment group and overall based on the Safety Analysis Set. A by-subject listing will be provided for all randomized subjects who violated at least 1 inclusion or exclusion criterion. The listing will include the criteria not met. A listing of subjects who received the wrong study drug will also be provided.

Protocol deviations occurring after subjects entered the study are documented during routine monitoring. The number and percentage of subjects with important protocol deviations by deviation reason and the total number of important protocol deviations by deviation reason (ie, nonadherence to study drug, violation of select inclusion/exclusion criteria) will be summarized by treatment group for the Full Analysis Set. A by-subject listing will be provided for those subjects with important protocol deviation.

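### The programming rule for actual treatment returns the randomised treatment for everyone dosed, so it cannot carry out the SAP's as-treated grouping

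*SAP*

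**What the plan says.** **Grouping rules.** SAP 3.2 groups the All Randomized set and the FAS as randomised. For the rest, "For other analyses, subjects will be grouped by actual treatment received". The same section says that actual and randomised treatment are to differ "only when the actual treatment received differs from randomized treatment for the entire treatment duration".

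The set definitions agree with this. For the Per Protocol set (SAP 3.1.3), "Subjects will be grouped according to the treatment they actually received". For the Safety set (3.1.4), "Subjects will be grouped according to the treatment they actually received. This is the primary analysis set for safety analyses". SAP 3.1.5.1 and 3.1.5.2 say the same for the hip and spine DXA sets, as do protocol 8.2.1.5 and 8.2.1.6.

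**Derivation.** SAP Appendix 12 item 6 begins "Randomized treatment (ie, TRT01P in ADSL) is derived from IXRSRAND". It then sets the actual-treatment variable, TRT01A, as "assigned as the randomized treatment if subject took at least 1 dose of study drug", and leaves it blank for anyone who took none.

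**Wrong-drug cases.** SAP 4.3 foresees them: "A listing of subjects who received the wrong study drug will also be provided".

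**The concern.** A variable named actual treatment should be able to differ from the randomised one. Item 6 uses the randomisation record and the fact of having taken a dose. It uses nothing about which drug was dispensed or taken, and it has no branch for the exception in 3.2. A programmer who follows it will produce Safety, PP and DXA tables grouped as randomised, under set definitions that promise as-treated grouping.

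At stake is the attribution of adverse events, renal data and BMD for any participant who took the other arm's drug throughout, and of that participant's follow-up time and any infection in the PP analysis. BMD and the renal measures at Week 48 make up the six key alpha-controlled safety endpoints (SAP 7.3.1, 7.4.1, 7.4.2, 7.4.4), and the DXA subset has only about 400 participants.

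**Working it through.** There is no planned figure to reproduce. The check sets the two rules side by side for each possible participant.

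| Participant | SAP 3.2 | Appendix 12 item 6 |
|---|---|---|
| Never dosed | Outside the Safety, PP and DXA sets | Blank |
| Dosed, randomised drug throughout | Randomised arm | Randomised arm |
| Dosed, other arm's drug for part of the time | Randomised arm | Randomised arm |
| Dosed, other arm's drug for the whole time | Other arm | Randomised arm |
| Dosed, two actives or two placebos throughout | Not defined | Randomised arm |

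The rules conflict in the fourth row. In the fifth, 3.2 is silent and item 6 settles the matter by default. The fifth row can arise because supply is double-dummy (protocol 3.3).

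**Is the exception handled elsewhere?** No other definition of TRT01A appears in the SAP. Sections 6.3 and 7.8, which record changes from the protocol, do not drop as-treated grouping. The variable is used: the exposure log-rank code in Appendix 12 item 13 stratifies by TRT01AN, which I take to be its numeric form. The other code samples use generic treatment names. That the Safety, PP and DXA tables use TRT01A is therefore an inference from the set definitions.

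**Size.** Let k be the number of participants in the fourth row. Under 3.2, k participants are regrouped. Under item 6 the number is 0, whatever was taken. The documents do not give k.

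- If k = 0, the two rules give identical tables.
- Each such participant is 1/5387 = 0.02% of the Safety set (5387 from SAP Appendix 3).
- A participant who is also in the DXA substudy is about 1/400 = 0.25% of it, or 1/200 = 0.5% of one arm (SAP 1.3.1 plans 200 per arm).
- In the PP on-treatment analysis (SAP 6.2.6), follow-up after permanent discontinuation runs to the last dose plus 10 days for F/TDF or plus 16 days for F/TAF. A misgrouped participant who discontinued gets the other window. The difference is 16 − 10 = 6 days, or at most 6/365.25 = 0.016 person-years. An infection diagnosed within those 6 days would be wrongly counted or wrongly left out.

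**PK.** The wording of 3.2 also reaches the PK sets. SAP section 8 says the PK analysis was done at the primary analysis and will not be repeated, so the consequence there is small for this analysis.

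**The case against.** The strongest reply is that item 6 is a programming note stating the default, that 3.2 governs, and that the exception is nearly empty. Much of this stands.

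- **The condition is narrow.** Someone treated to Week 96 has nine dispensing visits before it (Day 1 and Weeks 4, 12, 24, 36, 48, 60, 72 and 84; protocol Appendix 2). All would have to be wrong in the same direction. A single dispensing error could qualify only in someone who stopped very early and so contributed little data.
- **Item 6 may record a known fact.** The SAP was written after the primary analysis had been reported, and enrolment was complete. The sponsor may already have known that nobody met the condition. The SAP does not say so, however, and a reader cannot check an unstated finding.
- **The main efficacy result is safe.** The non-inferiority and superiority evaluations use the FAS, grouped as randomised (SAP 3.1.2, 6.2.5).

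A reader might infer that such an error would pass unseen. The documents do not support that, because the listing in 4.3 would show anyone given the wrong drug. What remains is that the listing does not move anyone in the tables.

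The appeal to 3.2 as the governing text does not remove the conflict. Item 6 gives a complete rule for every dosed participant and does not refer back to 3.2.

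**Conclusion.** The point holds as a contradiction within the SAP. As written, item 6 cannot carry out the grouping required by 3.2 and 3.1.3 to 3.1.5. Any participant on the other treatment for the whole period would sit in the wrong arm of the Safety, PP and DXA analyses, and could get the wrong on-treatment window.

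The importance is minor. The number affected is unknown and may be zero, and even a handful among 5387 would be unlikely to move the adverse event or renal comparisons materially. One case would weigh more in the DXA subset, or in a Fisher's exact comparison of proximal renal tubulopathy (SAP 7.4.6) if those events are rare.

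A reader might also infer that participants were in fact misclassified, or that the safety results are biased. The documents show neither: they plan a wrong-drug listing but give no count. The conclusion rests on reading item 6 literally and on TRT01A being the variable behind the as-treated tables.

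**What to change.** Amend Appendix 12 item 6 in one of two ways.

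1. Set TRT01A equal to TRT01P unless the IXRS bottle numbers (protocol 5.1), together with the drug accountability and administration records (SAP 4.2.3.1, 3.8.1), show that the active drug received was the other arm's for the entire treatment duration. State how participants with two actives, or with two placebos, throughout are classed. A rule based only on whether every bottle came from the other treatment would not settle those cases, because each arm is supplied with both tablet types.
2. If it has been checked and is true, state that no participant met the 3.2 condition, so that TRT01A equals TRT01P.

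The first option costs a few lines of dataset programming on data already collected. The 4.3 listing already requires wrong-drug cases to be identified. The second costs one sentence. Either should be settled in writing before the SAP is finalised, because the study was already unblinded for the primary analysis and the choice should not fall to whoever programs the tables.
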